We hypothesize that: 1) parents receiving the RTI[®] will have significant improvement in outcomes (psychological and physical health, self-management behaviors) compared with parents in the Attention Control arm, and 2) resourcefulness will mediate the effect of the intervention on all study outcomes.

Parent caregivers of children who require life-saving technology such as mechanical ventilation or feeding tubes must maintain a high level of vigilance 24 hours a day, 7 days a week, due to their child's potential for acute exacerbations and unknown illness trajectory. Their chronic stress related to caregiving while juggling household responsibilities affects their blood pressure, cortisol level,¹⁻³ sleep patterns,⁴⁻⁷ and overall physical health,^{2,8} compromises self-management behaviors⁹ and caregiving capacity,¹⁰⁻¹² and leads to more frequent emergency room (ER) visits and hospitalizations for the technology-dependent child.¹³⁻¹⁵ It is not surprising, therefore, that these caregivers report greater levels of stress and poorer psychological and physical health than do caregivers of Alzheimer's patients,¹⁶⁻¹⁸ which dramatically increases their mortality risk.^{19,20} Technology-dependent children (approximately 600,000) are among the sickest and most vulnerable subset of children with complex chronic conditions in the United States. They comprise 20% of all children discharged from the hospital to home,¹³ yet account for 61% of all healthcare spending for children,²¹ up to \$110 billion annually.²² Despite the adverse consequences, only psychoeducational interventions are employed to bolster parents' ability to manage stress and minimize the long-term negative effects on them and their children.

Self-management interventions based on cognitive-behavioral theory significantly decreases appraised stress and improves psychological, physical, and self-management outcomes in many caregiver populations.^{23,24,25,26,27} To date, no large scale study has tested such interventions with parents of these children to move the science forward as this study

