Children Who No Longer Require Technology. Parents whose children no longer require medical technology will remain in the study, and their data will be analyzed separately.⁴¹ We will document how soon after study enrollment the technology was discontinued. We expect about 5% will have technology discontinued and thus we will enroll additional participants to compensate for this attrition.

Retention Plans. To maximize retention over the 9 months, we will send birthday cards on the parent's and child's birthdays, as well as bi-monthly postcards with an inspirational message and contact information for the study office. Furthermore, we will recruit data collectors who are experienced and comfortable working with families who have children with special needs.

Controlling diffusion of intervention approaches. In our prior work, we found that few participants knew one another, so we believe the threat of diffusion is low. We recognize the possibility of the Hawthorne effect impacting our data. Therefore, the research team believes that it is vital to reliably track the amount of information and emotional support obtained by parents in all study arms and expect that any Hawthorne effect will be equally distributed because we are collecting the same information for both arms.

Measures. Study measures will be obtained at baseline (study enrollment), 6 weeks, and 3, 6, and 9 months post-enrollment, time frames selected based on prior work with caregivers and RTI[®] in order to capture variability over time. Table 2 shows study measures and measurement points. We chose measures based on our prior work with caregivers that are psychometrically sound and/or recommended by NIH as common data elements to facilitate cross-study analysis and increase the scientific impact of our study analyses.

Parent Outcome Variables: Parent Mental and Physical HRQoL will be measured by the 10-item Patient-Reported Outcomes Measurement Information System (PROMIS[®]) Short Form v.

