Aim 5: To assess the relationship between self-management behavior and parent psychological and physical health outcomes, we will use correlational and regression analyses. The effect of RTI[©] on outcomes will be estimated after controlling for important covariates in the structural equation model (SEM). Also, we will study parental psychological and physical health outcomes and its association with sleep (or positive health practices), using the SEM framework. The SEM is a general, flexible, powerful, and comprehensive methodology for representing, estimating, and testing a network of relationships among variables of interest. By the use of SEM, we will be able to develop a hypothetical model or path diagram that allows for specification of relationships and the directionality of the relationships among the variables of interest. These exploratory models or path diagrams that are derived from this study will be a basis for further study/validation. In the model fitting, we will use the method of maximum likelihood estimation (MLE) for estimating parameters.

To account for any multiple comparisons, a Bonferroni-corrected, two-sided significance level will be applied to all analyses for all aims. Additionally, we expect some level of missing data at each time point. To adjust for the missing data in all mixed-models analyses, we will apply pattern-mixture models to each model to ensure that missing data is adequately accounted for in each analysis. In contrast to a “completers only” approach, pattern-mixture models will provide a consistent and asymptotically efficient estimate of the effect of intervention on the monthly rate of change in parent outcomes when data is missing not at random.

Aim 6: We will analyze the technology-dependent children's ER visits, hospital days over 9 months using a Poisson regression model that adjusts for the intervention indicator variable and important covariates. This model will allow us to compare the relative rate of ER visits, hospital days between the two arms.

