Facebook and Twitter will be used to post the IRB flyer about the study. A "Friend" request will be sent to parent caregiver organizations who have members likely to meet inclusion criteria along with an introductory letter about our study and the request to post our recruitment flyer. The organization can make a decision to accept or reject the request to post our study flyer. Potential participants reached through either Facebook or Twitter would then self-identify and voluntarily contact us to hear more about the study and decide on participation. When they contact the study staff they will be screened for eligibility including residence within Northeast Ohio for face-to-face data collection.

Participants may receive some benefit from the stress reducing methods used in this study (Resourcefulness Training, writing in log). The potential risk for emotional distress is minimal and reasonable given the potential benefit for reducing stress and improving a parent's psychological and physical health outcomes and self-management behaviors (sleep, positive health practices). This study will benefit other families by aiding in our understanding of what methods help parents reduce stress and promote optimal psychological and physical outcomes and self-management behaviors when they are caring for a technology-dependent child. It is hoped that parents who participate in the

Resourcefulness Training arm of the study will feel more confident as they implement resourcefulness skills over the intervention period and will have a reduction in negative impact of caregiving over time. In addition, it is believed that the Resourcefulness Training intervention will enhance the care delivery by the parents and decrease the number of emergency room visits and hospitalizations.

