Possible causes for the participant to be withdrawn from the study include that the child with special medical technology has become too ill or has died. The participant may decide to withdraw from the study due to lack of interest to complete the remaining questionnaires at T2, T3, T4, T5 or that she/he is not interested in continuing to complete the journal writing. If the participant indicates an intent to withdraw from the study, she/he will be invited to share reasons for desire to withdraw from study. Participants will not be followed after they have voluntarily withdrawn from the study unless they indicate that they wish to be contacted in the future for any follow-up studies. If the child has the special medical technology removed during the course of their parent's participation in the study we will continue to conduct data collection but will note removal of technology in analysis.

There is no reimbursement for parking and meals but an incentive will be given to participants for their time and inconvenience. Participants will be given a \$25 gift card at each of 5 time points following completion and return of the questionnaires. The total payment will be \$125 over the study time if they complete all portions (5 data collection points) of the study. They will also receive a \$5 gift card each of the 4 time points they need to return the Actiwatch and sleep history booklet to the study office. The total payment for returning these items each time (4 time points) is \$20.

Data and safety monitoring will be conducted to determine if data collection should be altered or stopped. Every 6 months the DSM Committee will assess the risks and benefits of the study by reviewing individual adverse events and unanticipated problems that have occurred during the study. Data monitoring will include a review of the accuracy, validity, reliability and completeness of data collection. [name], the principal investigator will make the decision related to altering the study in collaboration with the committee if more than two mothers/fathers experience significant discomfort or distress that required a referral to United Way First Call.

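### A parent may be withdrawn because the child has become too ill, so outcomes can be lost from the families with the worst course, while parents whose child no longer needs technology stay in data collection

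*Combined protocol and SAP*

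**What the plan says.** The withdrawal paragraph, which comes just before the one on participant payments, covers three situations.

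- **Being withdrawn.** "Possible causes for the participant to be withdrawn from the study include that the child with special medical technology has become too ill"; the same sentence adds the child's death. It does not say what counts as too ill or who decides.
- **Choosing to leave.** The next sentence lists reasons for which the parent may decide to go. They include loss of interest in the remaining questionnaires, or that "she/he is not interested in continuing to complete the journal writing". Then: "Participants will not be followed after they have voluntarily withdrawn from the study", with an exception for contact about future studies.
- **Technology removed.** Here "we will continue to conduct data collection but will note removal of technology in analysis". The subsection Children Who No Longer Require Technology agrees: "Parents whose children no longer require medical technology will remain in the study, and their data will be analyzed separately".

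The background says that parents' chronic stress "leads to more frequent emergency room (ER) visits and hospitalizations for the technology-dependent child". The benefits paragraph expects the training to "decrease the number of emergency room visits and hospitalizations". Under Primary Analyses, Aim 6 reads: "We will analyze the technology-dependent children's ER visits, hospital days over 9 months using a Poisson regression model".

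Two safeguards are stated. The paragraph on multiple comparisons and missing data applies pattern-mixture models to the mixed-model analyses, with data missing not at random in view. The data and safety monitoring section tracks attrition with reasons and watches it by arm.

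**The concern.** Follow-up is protected when the child's need falls but not when the child gets worse. Severe illness in the child is not a neutral reason to stop observing a family. It goes with the parent stress and burden measured under Aim 1, and it produces the ER visits and hospital days counted under Aim 6. The plan also expects the intervention to reduce that healthcare use, so exit by this route may depend on something the treatment is meant to change. At stake are post-randomization outcomes from the families with the worst course and, if such exits differ between arms, some distortion of the comparison.

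**Working it through.** **Reading the text**

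1. The sentence on being withdrawn is separate from the sentence on what the parent may decide, so it is naturally read as withdrawal started by the study.
2. Removal of technology has an explicit rule: keep collecting. Death has a data step under Technology-Dependent Child Death: the date and cause are recorded. A child who becomes too ill has neither.
3. Pattern-mixture models cover the mixed models. Aim 6 is a Poisson regression, and no missing-data method is stated for it.
4. Monitoring attrition by arm reveals a loss but does not collect the missing outcomes.

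**The plan's own figure.** Sample Size and Justification needs 144 parents, expects 20-30% attrition and enrolls 210. 144/(1 - 0.30) = 205.7, or 206, so 210 reproduces closely. Expected losses are 210 x 0.20 = 42 to 210 x 0.30 = 63. At 30%, 210 x 0.70 = 147 remain, 3 above the 144 needed. How much of this attrition is due to a too-ill child is not stated.

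**Illustration for Aim 6. All inputs are assumptions.** Let a share p of families be withdrawn at 4.5 of 9 months. All families have a hospital-day rate of 1 per month up to then; the withdrawn families have rate k afterwards, and those later days are not recorded.

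Share of hospital days lost = 4.5pk / [9(1 - p) + p(4.5 + 4.5k)]

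| p | k = 2 | k = 5 | k = 10 |
|---|---|---|---|
| 0.02 (about 4 of 210) | 0.18/9.09 = 0.020 | 0.45/9.36 = 0.048 | 0.90/9.81 = 0.092 |
| 0.05 (about 10 of 210) | 0.45/9.225 = 0.049 | 1.125/9.90 = 0.114 | 2.25/11.025 = 0.204 |

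Follow-up time lost is p x 4.5/9, or 1.0% to 2.5%.

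**Arm comparison.** Suppose observed time is the offset (the plan does not say) and the arms differ only in p.

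- Equal p: true ratio = observed ratio = 1.00, so no bias.
- p = 0.02 in the training arm and 0.05 in control: the true ratio is 9.09/9.225 = 0.985, 9.36/9.90 = 0.945 or 9.81/11.025 = 0.890 for k = 2, 5, 10. The observed ratio is 1.00 each time.
- Shares reversed: the true ratio is 1.015, 1.058 or 1.124, and the observed ratio is again 1.00.

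**Against sampling error.** Assume a between-child coefficient of variation of 2 in hospital days and 105 per arm. Then SE(log ratio) = sqrt(2 x 4/105) = 0.28. Distortions of 1.015 to 1.124 are ln(1.015)/0.28 = 0.05 to ln(1.124)/0.28 = 0.42 of one SE.

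**Sensitivity.** If the families who leave already had rate k = 10 before exit, and p is 0.02 versus 0.05:

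- True ratio: (8.82 + 1.80)/(8.55 + 4.50) = 10.62/13.05 = 0.814.
- Observed ratio: (9.72/8.91)/(10.80/8.775) = 1.091/1.231 = 0.886.
- Distortion: 0.886/0.814 = 1.09, smaller than 1.124.

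**The case against.** **The wording is permissive.** It speaks of possible causes, and sparing a parent whose child is gravely ill is humane. Both points stand. But leaving the decision to the parent gives the same relief without a study-initiated exit.

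**The sentence on no further follow-up names voluntary withdrawal only.** This also stands. A reader might infer that the plan orders the outcomes of too-ill families to be discarded. It does not. Loss of later data is what being withdrawn from a study would ordinarily mean, but no rule states it. The consent pages are not in the copy available and could address it.

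**The plan anticipates informative missing data.** For the mixed models it does, and that lessens the concern there. It does not restore uncollected measurements, and it does not extend to the Aim 6 model.

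**The illustration is assumption throughout.** True. A split of 2% versus 5% is about 2 versus 5 families per arm, and Aim 6 is the last of six aims.

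Two stronger readings are tempting and should not be adopted.

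- *That training-arm parents who stop the log are put out of the study.* Leaving over the journal is the parent's choice. Follow-Up Contacts and Data Collection schedules T2 to T5 for both arms, the risk text lets a distressed parent stop writing, and missed entries are handled with reminders and counted as adherence. What is missing is one explicit sentence.
- *That withdrawal at Akron also ends access to the child's records*, because the recruitment text describes the release as covering the period of enrollment. The release form is not among the documents, so this cannot be established.

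**Conclusion.** The point holds as a gap in the withdrawal rule. The plan permits a parent to be withdrawn because the child is too ill, while it protects follow-up when technology is removed. That can lose outcomes from the families with the worst course, and for Aim 6 no stated method deals with the loss.

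The documents give no rate for such exits, so the size and direction of any bias cannot be calculated from them. Under the assumed rates, 2% to 20% of hospital days go unrecorded. The distortion of the rate ratio stays below half a standard error even with unequal exits, and is nil if exits are alike in both arms. Bias is probably modest. This is a cheap improvement and does not threaten the trial's validity.

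**What to change.** In the withdrawal paragraph:

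1. Remove the child's becoming too ill as a cause for the parent to be withdrawn. State that the parent decides whether to continue.
2. Before any full withdrawal, offer reduced follow-up: questionnaires only, permission to use the child's ER and hospital records to 9 months, or both.
3. As a minor clarification, state that stopping the log, boosters or calls does not end T2 to T5 data collection.

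The cost is consent and form wording, plus one more question to burdened families at a hard time. The T2 to T5 contacts and gift cards are already planned, and parents remain free to leave altogether.

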There are few risks to participants. A potential emotional risk during the interview is that recalling information regarding their child's course of illness and home management difficulties may make some parents uncomfortable. The interviewer will be vigilant to assess the parent's discomfort. Parents experiencing considerable discomfort will be asked if they wish to stop the interview and will be given supportive assistance by the interviewer. The parent will then be told to contact their primary care provider and given a resource sheet with the number of United Way First Call (211) to access on-call mental health professional services in their local area or Cuyahoga County 24-Hour Mental Health Crisis Information and Referral [contact]). If any participant is noted to have a level of depressive symptoms above the recognized clinical *T* score of 55.1 (raw score \geq 16- mild depressive symptoms) on the Patient-Reported Outcomes Measurement Information System (PROMIS) Short Form v 1.0-Depression 8a measure, he/she will be told of the findings and given instructions to contact his/her primary health care provider and the resource sheet with mental health contact phone numbers as above (See Mental Health Resources Decision Tree). Any parent expressing signs or symptoms of major depression (i. e., hopelessness and/or helplessness) in the enrollment interview, Resourcefulness Training appointment, telephone follow-up, journal writing, data collection appointments, booster sessions, or parents with a PROMIS-Depression 8a score of \geq 22 (moderate to severe depressive symptoms) or a Depressive Cognitions Scale score of \geq 7, will be assessed for imminent risk of suicide by asking if they have had any thoughts of harming

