themselves in any way or perhaps killing themselves. If the answer to any portion of the question is "yes" the participant will be told of a concern for their safety and the necessity for the interviewer to contact the Crisis Team from the Cuyahoga County 24-Hour Mental Health Crisis, Information and Referral Hotline immediately. The consent form will specifically discuss this risk. The research team members will notify the PI of any need to activate the above plans for the Crisis Team or referral to the 24-Hour Mental Health Crisis Information and Referral Hotline. Throughout the study, all research team members in contact with subjects will also assess for other psychiatric symptoms that might require intervention from the Crisis Team or the above 24-Hour Mental Health Hotline. Co-Investigators [name] and [name] are psychiatric nurses and can provide consultation to the Interventionist and data collectors when needed. Also, physical risks might involve fatigue due to the length of time (about 45 -50 minutes) needed to answer the study questions and about 1 hour for the Resourcefulness Training[®] intervention and practice journal entry. There is a slight inconvenience for all participants will need to take scheduled phone calls as per protocol, schedule time to meet with data collectors, wear Actiwatch at specified times and mail them back to study office. The intervention group will experience slight inconvenience due to time for intervention session, time to write in semi-structured journal 2-3 minutes daily for 4 weeks and 1 week booster journals (2 months, 4 months post intervention). Finally, there is a minimal risk to loss of confidentiality with collection of data particularly with the collection of Personal Health Information regarding the technology-dependent child. The consent form will specifically discuss these risks.

There is a slight risk of developing skin irritation from the Actiwatch. The participant will be instructed at enrollment that if any redness of the skin develops in the area where the watch is worn they are to remove it and contact the study office. There is also a very rare risk during hair sample collection of a minor scalp laceration (a cut) and infection related to same.

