All participants are volunteers and non-participation and withdrawal from the study are alternatives to study participation. Parents will be told that they may withdraw from the study at any time. There are no risks to non-participation or withdrawal from the study. The Project Director (at recruitment) and the data collectors (at enrollment) will explain that participation or non-participation will have no effect on the type, quality, or nature of medical care that the technology-dependent child receives, and that all research data will be obtained by an Interventionist or data collector and will not be communicated to any healthcare personnel at the healthcare facility.

Writing about the stress of caring for their child in their journal might bring out uncomfortable feelings. Parents will be instructed that if they experience distress, they may stop the journaling and contact the research staff. In addition, they will be instructed to tell the research staff about these feelings during the weekly follow-up telephone calls. If needed, we will provide emotional support and refer them to mental health resources such as the 24-Hour Mental Health Crisis, Information and Referral Hotline as detailed in the above description of risks. We have past experience teaching journal writing, analyzing journal entries, and reviewing entries for psychological distress. To minimize potential problems, we will collect journals after 1 month. Drs. [name] and [name], psychiatric-mental health nurses, will oversee online log writing analysis for high-risk mental health situations, and follow up as needed. In past experience with journal writing, no psychological distress has occurred. Additionally, we will make weekly follow-up phone calls for the first 4 weeks of the intervention to monitor for signs of psychological distress.

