Data and safety monitoring will be conducted to determine if data collection should be altered or stopped. Every 6 months the DSM Committee will assess the risks and benefits of the study by reviewing individual adverse events and unanticipated problems that have occurred during the study. The committee members are not part of the research team. This committee will review data on this study regarding 1) study safety, including auditing selected cases for compliance with IRB requirements, conformance with informed consent requirements, verification of source documents, and investigator compliance; 2) minimizing research-associated risk; and 3) protecting the confidentiality of participant data. In addition, it will review (1) all causes of mortality and (2) issues with participation. The rate of recruitment refusal (percent and reasons) and subject

attrition (percent and reasons) will be tracked and reported at these reviews. Differential attrition from the intervention and control arms also will be monitored. Written reports will be developed and submitted to the committee by the CWRU PI, [name], the principal investigator will make the decision related to altering the study in collaboration with the committee if more than two mothers/fathers experience significant discomfort or distress that required a referral to United Way First Call. [name] will be responsible to submit written reports to any funding agency within 2 weeks of the meeting. If concerns or problems are identified by the SMC, they will be reported to the IRB and funding agency via email by [name] within 3 business days after they are identified. If there are recommendations made by the SMC, the action plan for response or notice of any actions taken by the IRB regarding the research and any responses to those actions will be provided to Funding Agency Officials within 2 weeks.

References

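### The only numeric safety prompt counts referrals to United Way First Call; as worded it omits Crisis Team activations and does not clearly count crisis-hotline referrals

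*Combined protocol and SAP*

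**What the plan says.** The rule stands twice in the data and safety monitoring text near the end of the combined protocol and SAP, in the same words. The principal investigator decides about altering the study together with the committee "if more than two mothers/fathers experience significant discomfort or distress that required a referral to United Way First Call". No other referral destination is listed, and no other numeric safety prompt appears.

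The participant-risk text that follows the analysis section describes where distressed parents are sent:

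- **Discomfort in an interview.** Parents are told to contact their primary care provider and are "given a resource sheet with the number of United Way First Call (211) to access on-call mental health professional services". The sheet offers the county's 24-hour crisis line as the alternative. It also goes to parents with a PROMIS-Depression raw score of 16 or more.
- **Thoughts of self-harm.** The question is asked after signs of major depression in any study contact, a PROMIS-Depression score of 22 or more, or a Depressive Cognitions Scale score of 7 or more. A parent who answers yes is "told of a concern for their safety and the necessity for the interviewer to contact the Crisis Team", and contact is to be immediate.
- **Distress from log writing.** The text grants that "Writing about the stress of caring for their child in their journal might bring out uncomfortable feelings". If needed, staff will "refer them to mental health resources such as the 24-Hour Mental Health Crisis, Information and Referral Hotline", and the sentence then refers the reader back to the earlier account of risks.

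On reporting, team members are to "notify the PI of any need to activate the above plans for the Crisis Team or referral to the 24-Hour Mental Health Crisis" line.

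**The concern.** A numeric prompt is useful because it obliges someone to decide once a count is reached. It should therefore respond at least to the most serious events that the plan foresees. Here the count is tied to one named service. Read literally, three parents referred to First Call after considerable discomfort in an interview would require a decision, while three parents sent to the Crisis Team for thoughts of self-harm would not.

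Log writing raises a related question. Only the Resourcefulness Training arm writes logs, so this is the foreseen distress most specific to the intervention, and the service named for it is not the one in the rule.

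Participant protection is at stake, not the estimate of the treatment effect.

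**Working it through.** The plan states no figure to reproduce. The check sets the rule beside each referral route, all taken from the participant-risk and monitoring text.

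| Event | Destination named | Notice to the principal investigator stated? | Counts as worded? |
|---|---|---|---|
| Interview discomfort | Primary care provider; sheet with First Call or the county hotline | Not for First Call | Yes, if significant and referred to First Call |
| PROMIS-Depression raw score 16 or more | Primary care provider; same sheet | Not for First Call | Unclear: the rule asks for distress that required a referral, and the plan does not say whether handing over a sheet is one |
| Log-writing distress | Hotline as an example, with a pointer back to the earlier risk text | Yes, for the hotline | Yes if sent to First Call; no if sent to the hotline only |
| Thoughts of self-harm | Crisis Team | Yes | No |

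The threshold is more than two, so at least three parents. Applying it literally to different parents in each case:

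1. Three referred to First Call for interview distress: count 3, and 3 > 2, so the prompt is met.
2. Three Crisis Team activations without a First Call referral: count 0, not met.
3. Three log-distress cases sent only to the hotline: count 0, not met. The same three sent to First Call: count 3, met.
4. Two First Call referrals and two Crisis Team activations: count 2, not met. If both destinations counted, the count would be 2 + 2 = 4, met.

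Case 2 follows directly from the text. Case 3 depends on which service staff choose, and the log-writing sentence leaves that open.

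The routes can overlap. A PROMIS-Depression score of 22 or more is also 16 or more, so a parent who reaches the self-harm question that way also receives the sheet with the First Call number. A parent who reaches it through signs of hopelessness or the Depressive Cognitions Scale need not. In either case the Crisis Team activation itself is not what the rule counts.

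The reporting column shows a second mismatch. The reproduced text asks staff to report hotline referrals and Crisis Team activations, and nowhere asks them to report First Call referrals, which are what the rule counts.

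**The case against.** The strongest reply is that First Call is shorthand for the whole set of mental health resources. The interview route joins First Call and the county hotline with *or*. The log-writing sentence says *such as* and points back to that list. This is a fair reading for log distress.

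A reader might infer that the prompt cannot respond to log distress at all. The documents do not support that, because a log-distressed parent may be referred to First Call and would then count. The shorthand reading is weaker for self-harm, where the plan requires contact with the Crisis Team and does not offer First Call.

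A reader might also try to size the gap. Suppose 1% interview distress among 210 parents, all referred to First Call. The prompt is then met with probability P(Bin(210, 0.01) > 2) = 0.35 whatever the log-distress rate. If every log case counted, the probability would be 0.61, 0.90 or 0.98 at log-distress rates of 1%, 3% or 5% in the 105 parents of the training arm. These figures do not measure the gap. The rates are assumed, whereas the protocol reports no psychological distress in its past experience with journal writing. The constant 0.35 only restates the assumption that no log case reaches First Call. Crisis Team events are not in the calculation.

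Other safeguards are real:

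- The principal investigator is told of each hotline referral or Crisis Team activation.
- Weekly calls in the first 4 weeks monitor for distress, and psychiatric-mental health nurses oversee the log review.
- The committee reviews individual adverse events every 6 months, and that review can lead to a change without any count.

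It would therefore be wrong to infer that serious events go unseen. The adverse event protocol and the Mental Health Resources Decision Tree are not reproduced and may contain reporting steps, so the reporting mismatch holds only for the text available. What still stands is that the one rule with a count leaves out Crisis Team activations.

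**Conclusion.** The point holds, and it is minor. On the literal wording, Crisis Team activations for thoughts of self-harm do not count toward the only numeric prompt, and log-writing distress referred only to the hotline does not clearly count. The first part needs only the rule and the self-harm route as written. The second depends on how staff use a sentence that permits either service.

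The gap is confined to the prompt. Its size cannot be quantified, because the plan gives no rate of distress, referral or activation. Efficacy analyses are unaffected.

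**What to change.** In both places where the rule stands, extend the destination so that it covers a referral to First Call *or the 24-hour crisis hotline, or activation of the Crisis Team*. Then add three counting rules:

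- Each parent counts once.
- Every Crisis Team activation counts, however it was identified.
- A resource sheet given only because of a questionnaire score does not count.

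Keep the threshold of more than two. In the risk text, add First Call referrals for distress to the events that staff report to the principal investigator.

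The rule should not be limited to distress arising in a study procedure. That limit could exclude thoughts of self-harm found through a PROMIS-Depression or Depressive Cognitions screen, and it would ask staff for a judgement about cause.

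The cost is an edit to one sentence in two places and a few words in the risk text. Hotline referrals and Crisis Team activations are already reported, so only First Call referrals add reporting. Care for parents does not change. The downside is that the prompt may be met more often, including because of depression that predates the study. Since it opens a joint decision and does not stop the trial, that is acceptable.
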